3.3 Tertiary/Exploratory Endpoints

Correlataive studies: Defining a marker of disease activity in sensitized patients will have a significant impact on the future of desensitization protocols. Although DSA, cPRA, CDC and T cell and B cell flow crossmatch have been used to characterize the severity of sensitization, these assays are labor intensive and expensive. The proposed *plasma BAFF/APRIL ELISA* assays can be performed in 2-3 hours (1). We will determine whether these cytokines can reflect the immune response and predict response to desensitization and ultimately transplant outcome. *In addition*, we propose studies to address the effect of ixazomib on (a) *bone marrow derived BAFF/APRIL* generated by bone marrow-mesenchymal stem cells, knowing that these stromal cells play a key role during the maturation activation of plasma cells, (b) *bone marrow-derived antibody secreting cells (plasma cells)* (2) and (c) *plasma IgG subclasses, anti-HLA, ETAR, AT1R, and C1q antibody response to treatment* (3, 4).

BAFF/APRIL studies ([name] lab and [name] lab):

- These studies will be performed at time zero, prior to initiation of therapy, then every three months for 12 months.
- To define the range of BAFF/APRIL in sensitized patients, we will determine baseline levels and end of study levels in the sera and marrow obtained from peripheral blood and bone marrows of all 10 patients prior to treatment initiation. Higher BAFF/APRIL levels may be an indication of higher sensitization status.
- To determine whether serum BAFF/APRIL levels predict the level of sensitization, we will assess the correlation between BAFF/APRIL and other markers of sensitization in all 10 patients prior to treatment initiation. Using appropriate parametric and nonparametric statistical analyses we will determine whether BAFF or APRIL can independently predict cPRA, DSA and B cell flow crossmatch channel shift in case of transplantation to demonstrate the clinical value of these tests in defining sensitization intensity.
- To determine whether serum BAFF/APRIL levels predict treatment response, we will first determine if baseline serum BAFF/APRIL levels were higher in patients who failed to reach the primary or secondary endpoints. Next we will examine the correlation between BAFF/APRIL levels and outcomes using Pearson correlation coefficient analyses. Last, the effect of serum BAFF/APRIL on endpoints will be measured using Kaplan-Meier and Cox proportional-hazards models.
- To determine whether ixazomib therapy inhibits BAFF/APRIL generation by stromal BM-MSCs, we will determine if ixazomib inhibits BAFF/APRIL generation by BM-MSCs *in vivo*

and *in vitro* by (a) determining the difference in the production of BAFF/APRIL by BM-MSCs at enrollment and after study completion and (b) by measuring the direct effects of ixazomib on BAFF/APRIL generation in MSC cultures from pretreatment samples.

Antibody Secreting Studies ([name] lab):

- These studies will be performed at time zero prior to initiation of therapy, and at 12 months unless patients receive a kidney transplant. 10-60 mL of marrow will be collected from the iliac crest either in the transplant clinic or in the operating room right before the kidney transplant procedure.
- To determine the effect of treatment on bone marrow derived CD138⁺ plasma cells, we will (a) determine the difference in the percentage of bone marrow plasma cells at enrollment and after study completion (kidney transplantation or failure of desensitization) and (b) measure antibody secretion against the tetanus antigen and the three HLA peptides the patient is most sensitized against (c) conduct similar analyses to BAFF/APRIL studies described above in order to determine the level of sensitization and prediction to treatment response. These studies will be performed in collaboration with the laboratories of [name] and [name] laboratory as described previously (2, 37).

Antibody assays (Terasaki Research Foundation Laboratory)

- These studies will be performed at time zero, prior to initiation of therapy, then every three months for 12 months.
- As mentioned earlier, the critical issue for patient care is discerning which of the detected antibodies are pathogenic. In addition, the role of immunoglobulin subclasses in desensitization and kidney transplantation remains unknown. To address these questions, we propose to identify risk stratification strategies and to determine the pathogenic role and specificity of IgG subclasses, anti-HLA, non-HLA-DSA and complement fixing antibodies in desensitization.

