Sensitization in kidney transplant candidates. Alloantibodies (anti-HLA antibodies) arise through previous transplants, blood transfusions, and pregnancy. Currently, 39% of patients on the active kidney transplant waitlist are sensitized, evidenced by a Panel Reactive Antibody (PRA) $\geq 1\%$ (33). Of these, nearly 15,000 are highly sensitized, which means that they have a PRA $\geq 80\%$ (33). Transplant rates vary by PRA, ranging from 143.0 per 100 active waitlist years for candidates with a PRA of less than 1% to only 6.9 for those with a PRA of 98% or higher (33). Median waiting time for kidney transplantation in highly sensitized patients approaches 12 years, which is more than 3 times than for non-sensitized patients (33). As a result, a significant number of highly sensitized patients die before receiving a transplant, outlining the critical importance of desensitization strategies.

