4.2 Number of Patients

A total of 10 patients will be enrolled in this pilot clinical trial. We currently have more than 40 patients that qualify for the study based on the inclusion criteria described below. A patient will be considered enrolled after the first day of ixazomib treatment.

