7. STATISTICAL AND QUANTITATIVE ANALYSES

7.1 Statistical Methods

More than 50% of patients with CDC T cell crossmatch titers $\geq 1:8$ and/or cPRA $> 80\%$ fail to respond to desensitization (5, 8). In this pilot exploratory, proof of concept, open-label, single-center phase II clinical trial, we hypothesize that our study will have a higher rate of transplantation. [name], PhD, epidemiologist and biostatistician in the division of nephrology, will perform the statistical analyses. *Primary* efficacy (decline in cPRA $> 20\%$) and safety (discontinuation of therapy due to adverse events) endpoint will be analyzed using the exact binomial test. The *secondary* endpoint (time to transplantation) will be assessed using Kaplan-Meier analyses and log rank tests. Baseline characteristics will be compared between participants with and without the primary end point using the 2-sample t test for continuous variables and the Fisher's exact test for categorical variables. Relationships between serum BAFF/APRIL, antibodies, and baseline cPRA will be assessed using the Pearson correlation coefficient. The influence of serum BAFF/APRIL, antibodies, and bone marrow plasma cells on end points of interest will be investigated using Kaplan-Meier curves and Cox proportional-hazards models.

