7.1.1 Determination of Sample Size

The primary outcome will be considered as a dichotomous outcome (decline in cPRA of $>20\%$ or not). We will test the hypothesis that the success rate (i.e., the % that have a decline in cPRA $>20\%$) is 0% using the exact binomial test (Figure 2a) (5). The figure shows the lower and upper 95% confidence limits resulting from any observed success rate. For example, if we observe success in 3/10 (30%), the resulting 95% confidence interval (CI) is (6.7%, 65.2%). Any observed success demonstrates that the success rate of the proposed treatment is >0 . Figure 2b represents the power curve, that is, the probability of observing any success, given different values of true success rate. For example, we would have $> 80\%$ chance of observing at least one success if the true success rate is > 0.2 .

Figure 2a. Sample Size Analysis

[figure not shown]
[figure not shown]

Figure 2b. Power curve

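### The Section 3.3 response analyses do not condition on Day 1 cPRA, so a BAFF/APRIL marker that only mirrors baseline sensitization could be reported as predicting response

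*Combined protocol and SAP*

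**What the plan says.** Section 3.3 sets out three steps for judging whether serum BAFF/APRIL predicts response:

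- a group comparison: "we will first determine if baseline serum BAFF/APRIL levels were higher in patients who failed to reach the primary or secondary endpoints";
- a correlation: "Next we will examine the correlation between BAFF/APRIL levels and outcomes using Pearson correlation coefficient analyses";
- Kaplan-Meier and Cox models for the endpoints.

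Section 7.1 repeats the last step: "The influence of serum BAFF/APRIL, antibodies, and bone marrow plasma cells on end points of interest will be investigated using Kaplan-Meier curves", together with Cox models. Neither section names baseline cPRA, or any other covariate or stratum, for these analyses. The first two steps are two-variable by construction. For the Cox model the covariates are simply not stated.

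Section 3.3 also states the expected link between marker and sensitization: "Higher BAFF/APRIL levels may be an indication of higher sensitization status". Where it speaks of independent prediction, it means prediction of cPRA, DSA and crossmatch, not of response.

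Baseline cPRA does appear elsewhere. Section 7.1 correlates BAFF/APRIL with baseline cPRA. It also compares baseline characteristics, which Section 7.1.5 lists as including baseline cPRA, between patients with and without the primary endpoint. No planned analysis takes marker, baseline cPRA and response together.

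**The concern.** Baseline sensitization may drive both the marker level and failure. The plan supplies the first link itself. For the second, Section 1.9 reports transplant rates per 100 active waitlist years falling from 143.0 at a PRA below 1% to "only 6.9 for those with a PRA of 98% or higher". Sections 1.1.1 and 1.9 report that an earlier regimen failed above a cPRA of 90%. If both links hold in this trial, failures can show higher BAFF/APRIL even when the marker says nothing beyond the cPRA already on file.

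Section 2.2 makes it an aim to find indices that separate responders from non-responders, and it looks to biomarkers and surrogate endpoints for a follow-on trial. What is at stake is carrying forward a marker that duplicates a measurement every enrolled patient already has. The same gap reaches the plasma-cell studies, because Section 3.3 gives them analyses similar to those for BAFF/APRIL.

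**Working it through.** **1. The plan's own figures.** Section 4.2: "A total of 10 patients will be enrolled in this pilot clinical trial". Section 7.1.1: "if we observe success in 3/10 (30%), the resulting 95% confidence interval (CI) is (6.7%, 65.2"%). The exact (Clopper-Pearson) limits are the 2.5% point of Beta(3, 8) and the 97.5% point of Beta(4, 7), which are 6.67% and 65.25%. The same section claims a better than 80% "chance of observing at least one success if the true success rate is > 0.2". At 0.2 the probability is 1 − 0.8^10 = 0.893. Both figures reproduce. The documents give no power or effect size for the BAFF/APRIL analyses, so the correlations, the 30% responder share and the 5% level below are assumptions.

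**2. Thresholds at n = 10 (two-sided 5%).** Significance needs |r| ≥ t/√(df + t²).

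- Unadjusted, 8 df, t = 2.306: 2.306/√(8 + 5.318) = 0.632.
- Adjusted for one covariate, 7 df, t = 2.365: 2.365/√(7 + 5.592) = 0.666.

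**3. A pure mirror of cPRA.** Let C be baseline cPRA, standardised. Marker M = ρC + √(1−ρ²)·e₁ and outcome Y = bC + √(1−b²)·e₂, with independent errors. Then corr(M, Y) = ρb, while the partial correlation given C is 0. Simulated over 40,000 trials per setting; the t test uses trials with at least two patients in each group, about 85% of them.

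| ρ / b | ρb | Pearson, unadjusted | t test of marker by response | Partial correlation given C |
|---|---|---|---|---|
| 0.3 / 0.3 | 0.09 | 5.6% | 5.5% | 4.8% |
| 0.5 / 0.5 | 0.25 | 10.7% | 8.4% | 5.0% |
| 0.7 / 0.7 | 0.49 | 31.5% | 19.9% | 5.0% |
| 0.9 / 0.9 | 0.81 | 88.3% | 57.8% | 5.0% |

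**4. The same question with rank methods** (4,000 trials per setting). Sensitization S is standard normal, the marker has correlation 0.5 or 0.7 with S, and logit P(response) = −0.6 − βS with β = 1, 2, 3.

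- One-sided exact Mann-Whitney for a higher marker in failures: 11%, 15%, 20% at correlation 0.5, and 15%, 28%, 37% at 0.7. The mean marker difference is 0.42 to 0.97 SD.
- Continuous outcome, decline = −(β/2)S + unit-variance noise. The implied sensitization-outcome correlation is (β/2)/√(1 + β²/4), that is 0.45, 0.71 and 0.83 in size. Unadjusted Spearman is falsely significant in 9.5% to 40% of trials, and the partial rank correlation given S in 5.3% to 6.9%.

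**5. Would the separate analyses in Section 7.1 reveal a mirror?** Only some of the time. At ρ = b = 0.7, the marker-cPRA correlation is significant in 68% of trials and the t test of baseline cPRA by response in about 40%.

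**6. What adjustment costs.** With 7 df, a true partial correlation of 0.5 is detected in 29% of trials, 0.7 in about 61%, and 0.8 in 82%.

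**7. Events for the Cox model.** If the untreated rate of 6.9 per 100 years applied (an assumption), expected transplants in 12 months would be 10 × (1 − e^(−0.069)) = 0.67. A Cox model for transplantation could then barely support the marker, let alone a second covariate.

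**The case against.** The strongest reply is that Section 3.3 promotes BAFF/APRIL as a quick ELISA in place of slower, costlier assays, cPRA among them. On that rationale a marker that mirrors cPRA, and so forecasts failure, is partly the hoped-for result, and prediction as such does not require freedom from confounding. That is fair as far as measuring sensitization goes. It does not settle the response question. Every enrolled patient already has a known cPRA, so a marker that only repeats it adds nothing for identifying responders.

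A reader might infer that the plan ignores baseline cPRA. It does not: Section 7.1 plans both legs of the triangle, marker with cPRA and cPRA with the primary endpoint. What is missing is the joint look.

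A reader might also infer that a mirror marker will be reported as predictive. The figures do not support that. In the 0.5 to 0.7 range most simulated trials would not flag it, and Section 3.3 names neither a significance level nor a test for the group comparison. The link from cPRA to outcome is indirect as well. The waitlist rates contrast PRA below 1% with 98% or higher, while Section 5.1 admits only cPRA of 80% or more. The failure above 90% concerns IVIG and rituximab. The documents give no cPRA gradient for ixazomib.

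Finally, requiring the adjusted association to be significant before claiming prediction would discard many real markers at this sample size. That objection stands and shapes the fix.

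**Conclusion.** The point holds as a minor one. The response analyses do not condition on Day 1 cPRA, and no planned analysis combines marker, baseline cPRA and response, so a marker that mirrors baseline sensitization could be presented as predicting response. The false-flag rate is roughly 10% to 40% with marker-sensitization correlations of 0.5 to 0.7 and a moderate to strong link from sensitization to outcome, against about 5% to 7% with adjustment. With both correlations near 0.3 the inflation is negligible. All these correlations are assumed, and the restricted cPRA range may weaken them.

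Adjustment does not address a separate limit. With one treated arm, even an adjusted association cannot separate response to ixazomib from general prognosis, so neither a predictive nor a surrogate claim can rest on it. The analyses are listed as exploratory in Section 3.3, although Section 2.2 places them under the secondary objectives. The primary efficacy and safety conclusions are not affected.

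**What to change.** In Sections 3.3 and 7.1:

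- Keep the unadjusted results. Beside them, report the partial rank correlation, with permutation p-value and interval, between baseline BAFF or APRIL and each patient's change in cPRA and in MFI, controlling for Day 1 cPRA. Treat the plasma-cell measures the same way where Section 3.3 extends these analyses to them.
- Add a per-patient table or plot of marker, Day 1 cPRA and outcome.
- State which covariates, if any, enter the Cox models.
- Do not make significance of the adjusted test a pass/fail condition. The named downside of adjustment is low power at n = 10, so a null adjusted result does not rule a marker out.
- Describe any finding as a hypothesis-generating association with outcome under treatment, not as prediction of response to ixazomib or as a surrogate endpoint, and align the wording of Section 2.2.

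The cost is a few sentences, one more analysis line and one degree of freedom. Day 1 cPRA is already in the schedule of events and MFI change is already planned in Section 7.1.6, so no new data are needed.

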4. STUDY DESIGN

4.1 Overview of Study Design

Recruitment

Two avenues of recruitment will be followed.

- The first option is when the physician of a patient who has a cPRA < 80% and has been on the kidney transplant list for over 24 months, believes the patient is an eligible candidate for this study, the patient's physician or other clinical personnel involved in the care of the patient will describe the study to the patient. If the individual is interested, has provided permission for their name and contact information to be shared with the study team, and agrees to be contacted by the study team, the study team may contact the individual either in person (at this visit) or via telephone or e-mail (after this visit). If study personnel are available to meet with the potential subject in clinic, the study personnel will explain the study thoroughly and ask the potential subject if they are interested in hearing more information. If so, the study personnel will continue and review the consent form, answering questions and concerns. If the patient is comfortable with the study, they can sign the consent form at that time or they may take the consent form home for further review and finalize consent at a later date. If the study team is not available to meet with the potential subject in the clinic, the study team will follow-up by telephone. If the study discussion occurs via phone, the informed consent document and authorization form will be mailed to the potential subject for review.
- The second option for potential subject identification is to pre-screen highly sensitized patients (cPRA ≥ 80%) on the kidney transplant waitlist (> 24 months) in the Transplant

Database. If a potential subject is identified, the subject will be sent a letter of introduction that includes information about the study and informs them that they will receive a phone call from a member of the study team to discuss the details of the study, and provides contact information to opt out of receiving the phone call.

Use of E-mail: E-mail will be used as a means of communicating with subjects two different ways;

1. E-mail may be used to schedule the initial study visit. After the subject has had the study introduced to them through a physician or other clinical personnel involved in their clinical care, the study team will e-mail them using the template provided in the recruitment section.
2. E-mail may be used throughout the course of the study for the purpose of scheduling study visits and notifying subjects of other study-related information.

Study Procedures

Screening Visit

The screening visit procedures will occur within a 30-day window prior to the Visit 1, Cycle 1 window (3-month window after screening). The following procedures will occur at the screening visit:

- Physical exam
- Medical history (including most recent cPRA results prior to enrollment)
- Vital Signs (Temperature, pulse, respirations, and blood pressure)
- Medication History
- Pregnancy Test (Serum HCG) for females of child-bearing potential
- CBC
- LFTs

Re-screening

Subjects who fail screening may be considered for re-screening if, in the opinion of the principal investigator, their clinical status has changed such that they may now be eligible for study participation per all eligibility criteria. At the discretion of the principal investigator, selected tests, such as lab tests, will not be repeated if previous screening results remain valid per the protocol-defined window for that test.

Visits: Patients will only receive one month's supply of ixazomib and dexamethasone and will return monthly for resupply. At each visit, they will be assessed for AEs by the study team. They will be examined by the principal investigator 5 times (please see tables 2-1 a-b and Figure 1, below): Days 1, 85, 169, 253, and 373 +6, - 3).

- Day 1: Prior to treatment initiation. H&P, Labs, Bone Marrow Aspirate
- Day 85 + 6, - 3: Prior to treatment dose. H&P, Labs
- Day 169 + 6, - 3 Prior to treatment dose. H&P, Labs
- Day 253 + 6, - 3 Prior to treatment dose. H&P, Labs
- Day 373 + 6, - 3 One month after treatment completion, H&P, Labs, Bone Marrow Aspirate
- Study drug will be dispensed at each month's in-person visit, prior the initiation of the next cycle, and after reviewing the AEs and monthly labs.

- Liver Function tests will be conducted twice a month (+ 6 /- 3 days) for the first 3 months, then monthly thereafter. The complete blood count (CBC) will be checked monthly. cPRA, BAFF/APRIL, DSA and antibodies will be checked every three months (5 times total). Bone marrow aspirates will be collected at the beginning and at one of the following endpoints: one month (+6, - 3 days) after the end of the 12 month study, cPRA decline > 20%, time of transplant, or time of subject withdrawal from the study. ECG and echocardiograms will be done at the baseline, 6 months, and end of the study visits.
- During the first three months of study participation, the bi-weekly Liver Function Tests may be done at the subject's local lab. The local lab will process the sample and send the result to the study team.
- Additional visits may be required if the subject has to hold treatment and needs to return to the clinic for blood draws to confirm eligibility to continue. Please see Table 4-3, Dose Adjustments for Hematologic Toxicities for dose adjustment plan.
- Data on acute rejection, graft and patient survival will be collected for six months after surgery for those subjects who receive a successful kidney transplant.

[figure not shown]
Unscheduled Visits: Subjects may have unscheduled visits due to dose adjustments based on lab results, an acute illness of undetermined cause, for other reasons, or at the discretion of the Investigator. Unscheduled visits may include any of the following procedures;

- Adverse Event Assessment
- Medication History
- Drug Accountability
- Physical Exam
- Vital Signs (Temperature, Pulse, Respirations, Blood Pressure)
- Lab work (CBC, LFTs, cPRA, BAFF/APRIL, DSA Antibodies)
- Bone Marrow Aspiration

Early Termination Visit: All subjects who end study participation prior to the end of the scheduled treatment will undergo an early termination visit within one week from study discontinuation. The early termination visit will consist of the following procedures;

- Adverse Event Assessment
- Medication History
- Drug Accountability
- Physical Exam
- Vital Signs (Temperature, Pulse, Respirations, Blood Pressure)
- Lab work (CBC, LFTs, cPRA, BAFF/APRIL, DSA Antibodies)
- Bone Marrow Aspiration (bone marrow aspiration will be done within 48 hours of transplant)

Figure 1. Study Overview Diagram

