Table 1-1 IXADES Treatment Protocol

| 28-Day Cycle (a 4-week cycle) | | | | | | | | |
|-------------------------------|--------|----------|--------|-----------|--------|------------|--------|------------|
| | Week 1 | | Week 2 | | Week 3 | | Week 4 | |
| | Day 1 | Days 2-7 | Day 8 | Days 9-14 | Day 15 | Days 16-21 | Day 22 | Days 23-28 |
| Ixazomib (NINLARO) 3 mg | ✓ | | ✓ | | ✓ | | | |
| Dexamethasone 20 mg | ✓ | | ✓ | | ✓ | | | |

Figure 1. Study Overview Diagram

Ixazomib for Desensitization (IXADES) in Kidney Transplantation

SCHEDULE OF EVENTS
Table 2-1 (a)-Schedule of events (first six cycles)

| Procedures Performed | Screening (<=/ 30 days) | Cycle 1 (< /= 3 months after screening) | | | Cycle 2 | | Cycle 3 | | | Cycle 4 | | | Cycle 5 | | | Cycle 6 | | |
|------------------------------------|-------------------------|---|---|----|---------|----|---------|----|----|---------|----|----|---------|-----|-----|---------|-----|-----|
| | | 1 | 8 | 15 | 29 | 36 | 43 | 57 | 64 | 71 | 85 | 92 | 99 | 113 | 120 | 127 | 141 | 148 |
| Treatment Days (+6, -3) | | | | | | | | | | | | | | | | | | |
| Ixazomib and Dexamethasone | | X | X | X | X | X | X | X | X | X | X | X | X | X | X | X | X | X |
| Medical History | X | X | | | | | | | | | X | | | X | | | X | |
| Physical Exam | X | X* | | | | | | | | | X | | | | | | | |
| Vital Signs (T, P, R, BP) | X | X | | | X | | | X | | | X | | | X | | | X | |
| AE Assessment | | X | | | X | | | X | | | X | | | X | | | X | |
| Electrocardiogram (ECG) | X | | | | | | | | | | | | | | | | | |
| Echocardiogram | X | | | | | | | | | | | | | | | | | |
| Medication History | X | X | | | X | | | X | | | X | | | X | | | X | |
| Drug Accountability | | | | | X | | | X | | | X | | | X | | | X | |
| Pregnancy Test (where appropriate) | X | | | | | | | | | | | | | | | | | |
| CBC | X | X | | | X | | | X | | | X | | | X | | | X | |
| LFTs | X | X | | X | X | | X | X | X | | X | | | X | | | X | |
| cPRA | | X | | | | | | | | | X | | | | | | | |
| BAFF/APRIL | | X | | | | | | | | | X | | | | | | | |
| DSA Antibodies | | X | | | | | | | | | X | | | | | | | |
| Bone Marrow Aspiration | | X ¹ | | | | | | | | | | | | | | | | |

*Physical examination to be completed at visit 1, if not completed during screening visit.

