5.2 Exclusion Criteria

Exclusion criteria: Patients will be excluded from the study based on the following criteria:

- (1) Female patients who are lactating or have a positive serum pregnancy test during the screening period
- (2) Major surgery requiring hospitalization within 6 months before enrollment
- (3) Infection requiring systemic antibiotic therapy or other serious infection within 14 days before study enrollment
- (4) Evidence of current uncontrolled cardiovascular conditions, including uncontrolled hypertension, uncontrolled cardiac arrhythmias, symptomatic congestive heart failure, unstable angina, or myocardial infarction within the past 6 months
- (5) Systemic treatment, within 14 days before the first dose of ixazomib, with strong CYP3A inducers (rifampin, rifapentine, rifabutin, carbamazepine, phenytoin, phenobarbital), or use of St. John's wort
- (6) Any serious medical or psychiatric illness that could, in the investigator's opinion, potentially interfere with the completion of treatment according to this protocol
- (7) Inability to take oral medication
- (8) Diagnosed or treated for another malignancy within 2 years before study enrollment or previously diagnosed with another malignancy and have any evidence of residual disease. Patients with nonmelanoma skin cancer or carcinoma in situ of any type are not excluded if they have undergone complete resection
- (9) Grade 2 or greater peripheral neuropathy according to NCI Common Terminology Criteria for Adverse Events (CTCAE)
- (10) Participation in other desensitization therapies or investigational drug clinical trials, including those with other investigational agents not included in this trial, within 6 months of the start of this trial and throughout the duration of this trial
- (11) Patients that have previously been treated with ixazomib, or participated in a study with ixazomib whether treated with ixazomib or not
- (12) Active or treated infection for HIV, HCV or HBV

- (13) History of Liver cirrhosis, biopsy confirmed
- (14) Elevated transaminases (greater than 3 times the upper limit of normal)
- (15) Known hypersensitivity to ixazomib
- (16) Active substance abuse by self-report or medical record
- (17) Electrocardiography evidence of acute ischemia or active conduction system abnormalities

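### The 30-day and 3-month screening limits have no clear anchor, so the pregnancy test and ECG, which are not repeated on Day 1, can be about 3 to 4 months old at first dose

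*Combined protocol and SAP*

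**What the plan says.** Section 4.1 (Screening Visit) states: "The screening visit procedures will occur within a 30-day window prior to the Visit 1, Cycle 1 window (3-month window after screening"). The column headings of Table 2-1(a) carry the same two limits, "Screening (<=/ 30 days") and "Cycle 1 (< /= 3 months after screening"), and the first of these names no end point.

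Table 2-1(a) marks the pregnancy test in the screening column only, and the row is empty for the rest of Tables 2-1(a) and 2-1(b). Exclusion 1 in section 5.2 removes "Female patients who are lactating or have a positive serum pregnancy test during the screening period". The ECG is marked at screening and next at Cycle 7. The screening list in section 4.1 omits it, and later in that section it is placed at an undefined baseline visit. Exclusion 17 depends on it.

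For the physical exam, the footnote to Table 2-1(a) reads: "Physical examination to be completed at visit 1, if not completed during screening visit". Sections 4.1, 7.1.8 and 9.1 list a history and physical on Day 1 before treatment, with no such condition.

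The re-screening paragraph of section 4.1 says that selected tests "will not be repeated if previous screening results remain valid per the protocol-defined window for that test".

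**The concern.** Two limits are given for what looks like one interval, and the text does not say how they fit together. A patient whose first dose falls 60 days after screening is within one limit and outside the other if the 30 days runs to Day 1.

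This matters for results that decide eligibility and are not refreshed before dosing. Exclusion 1 is met by any negative test in the screening period, however long ago, so a woman who conceived between screening and Day 1 would still pass the test-based criterion. Section 6.6 says the drug's effect on human pregnancy is not known, and section 8.3 requires permanent discontinuation if pregnancy occurs. The ECG criterion has the same gap.

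There is also a measurement issue. Section 3.1 includes distal neuropathy in the primary safety endpoint, and Table 4-3 uses return to baseline when deciding on further dosing. If the footnote governs, the last examination before treatment may be the screening one.

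**Working it through.** The plan states no design figure for this point, so there is none to reproduce. The check is date arithmetic on the stated limits, followed by a comparison of the screening and Day 1 columns.

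**Inputs.** 30 days and 3 months (section 4.1; Table 2-1(a) headings). Three calendar months last 89 to 92 days, depending on the start month. The visit tolerance of +6/−3 days is not added, because section 7.1.8 exempts visit 1.

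**Maximum age of a screening-only result at first dose.**

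| Reading | Formula | Result |
|---|---|---|
| A. The 30 days runs to Day 1 | 30 | 30 days |
| B. First dose within 3 months of the screening procedure | 3 months | 89–92 days |
| C. Screening period of up to 30 days, then a 3-month start window | 30 + (89 to 92) | 119–122 days |

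B is about 3 times A (89/30 = 2.97; 92/30 = 3.07). C is about 4 times A (119/30 = 3.97; 122/30 = 4.07). If the +6 tolerance did apply to Day 1, the results would be 36, 95–98 and 125–128 days.

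**Which results can reach that age.** Comparing the two columns of Table 2-1(a):

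- Marked at screening and again on Day 1: CBC, LFTs, vital signs, medical history, medication history. These are current at first dose under every reading.
- Marked at screening and not on Day 1: pregnancy test, ECG, echocardiogram. The pregnancy test supports exclusion 1 and the ECG supports exclusion 17. No entry criterion names the echocardiogram, so it is left out of the conclusion.
- Marked on Day 1 with a condition: physical exam.

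**Physical exam.** The footnote requires it at visit 1 only if it was not done at screening. Sections 4.1 and 9.1 list a Day 1 history and physical before treatment, and section 7.1.8 says a physical exam takes place at each of its five listed visits, the first being Day 1. A site working from the schedule can omit what the text requires.

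**Re-screening.** The rule depends on a validity window for each test. No test has one, and the general window has three readings.

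**The case against.** The strongest reply is that the limits are not contradictory. The text and the table give them in the same order, and a screening period of up to 30 days followed by a start window is a coherent design. That is correct: the limits conflict only if the 30 days is counted to Day 1. But nothing in the text selects the sequential reading, and it is also the most permissive, at about 4 months.

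A reader might infer that patients are dosed on stale eligibility data generally. The documents do not support that. Day 1 repeats the CBC and LFT panels along with vital signs, medical history and medication history. Exclusions 2, 3 and 8 are tied to enrollment, which section 4.2 places after the first day of ixazomib, and exclusion 5 is tied to the first dose. Exclusion 4 asks about current conditions.

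A reader might also infer that no physical exam is done on Day 1. Three sections schedule one, so the fault is a conflict between footnote and text.

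On pregnancy, sections 5.1 and 6.6 require women of childbearing potential to agree to two contraceptive methods or true abstinence from the signing of consent, which covers the gap before dosing. Section 1.10 has the investigator sign an eligibility checklist before drug is dispensed. Both reduce the risk, but neither verifies pregnancy status at first dose, and section 1.10 asks for no repeat test.

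On neuropathy, the grades in Table 4-3 rest largely on symptoms and daily function, which the Day 1 history can capture. That weakens the claim of a biased baseline but does not settle which instruction a site should follow.

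**Conclusion.** The point holds in a limited form. The screening-to-dose interval is ambiguous, with maxima of 30, 89–92 or 119–122 days. Under the two longer readings, the pregnancy test and the ECG can be about 3 to 4 months old at first dose; under the shortest they cannot. The physical exam could be equally old only if the footnote overrides sections 4.1, 7.1.8 and 9.1.

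This assumes that sites follow Table 2-1(a) as printed and add no tests of their own. The documents do not show how often starts would be delayed or how many participants could become pregnant, so no event rate can be given. With 10 patients, one pre-existing finding counted as arising on treatment is 1/10 = 10% of the sample. That is the weight of a single case and says nothing about how likely it is.

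The point does not affect the sample size or the efficacy analysis. It is worth correcting because it bears on participant safety and on the pre-dose safety baseline.

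**What to change.** 1. State one maximum interval from the screening procedures to the first dose, in the same words in Table 2-1(a) and section 4.1, and say which event starts and ends it. The length is for the sponsor to choose.
2. Require the negative serum pregnancy test and the ECG to fall within that interval before the first dose, and to be repeated if it is exceeded. An hCG can use the blood already drawn on Day 1, provided the result is available before dosing. Add the ECG to the screening list in section 4.1.
3. Reword exclusion 1, in section 5.2 and in the Protocol Summary, to refer to that interval, and make the re-screening rule point to it.
4. Reconcile the Table 2-1(a) footnote with sections 4.1, 7.1.8 and 9.1 so that a pre-dose exam, with a neuropathy grade recorded, supplies the baseline.

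The cost is a wording amendment and an occasional repeat pregnancy test or ECG when a start is delayed. The Day 1 exam is already scheduled in the text.
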